4.1 Selection of Study Population

4.1.1 Inclusion criteria

Patients who fulfill the following criteria will be included in the study. If the patient eligibility is uncertain, the investigator should discuss enrollment of the patient with a medical monitor prior to randomization.

- 1) Patients who were fully informed of and understand the objectives, procedures, and possible benefits and risks of the study and who provided written voluntary consent to participate in the study. If the patient is a minor at the time of consent, written consent should be obtained from a legally acceptable representative (guardian) in addition to the patient him/herself.
- 2) Outpatients aged 18 through 74 years at the time of consent.
- 3) Patients with bipolar I disorder, most recent episode depressed, with or without rapid cycling disease course (≥ 4 episodes of mood disturbance but < 8 episodes in the 12 months prior to screening), and without psychotic features (diagnosed by DSM-IV-TR criteria and confirmed by the Mini International Neuropsychiatric Interview [MINI]).
- 4) Patients who have a history of at least one manic or mixed episode (preferably with confirmation by a reliable informant, such as a family member or caregiver).
- 5) Patients whose current major depressive episode is ≥ 4 weeks and < 12 months in duration at screening.
- 6) Patients with a rater-administered MADRS total score of ≥ 20 and a computer-administered MADRS total score of ≥ 20 at both screening and baseline.
- 7) Patients with a YMRS total score of ≤ 12 at both screening and baseline.
- 8) Patients with a negative pregnancy test at screening, when the patients are female and of childbearing potential.
- 9) Patients who agree to use appropriate contraception (see Section 5.6, Page 44) to prevent pregnancy in female patients and the female partners of patients, when the patients or their partners are of childbearing potential.

- 10) Patients whose dosage of the following concomitant drugs remains unchanged for the specified duration as follows:
- The dose of oral hypoglycemic drugs or antihypertensive drugs remained unchanged for at least 30 days prior to screening.
 - The dose of thyroid hormone (replacement therapy) remained unchanged for at least 90 days prior to screening.
 - The dose of drugs for complications (other than the above-mentioned drugs) have been stable (within $\pm 25\%$) for at least 30 days prior to screening.

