- 17) Patients with previous or existing clinically significant complications, such as serious nervous system, endocrine system (eg, type I diabetes mellitus), hepatic, renal, hematological, respiratory, cardiovascular (eg, unstable angina, congestive heart failure), gastrointestinal, urological, or other diseases. Patients who have a history of any of such diseases and who are considered ineligible for the study by the investigator.
- 18) Patients with acute hepatitis, severe chronic hepatitis or marked hepatic dysfunction. When the hepatitis screening test is positive, the investigator should evaluate carefully patient eligibility on the basis of his or her medical history or other laboratory data.
- 19) Patients with a gastrointestinal disease or a surgical history that may affect drug absorption, distribution, metabolism, or excretion.
- 20) Patients with any chronic organic disease of the central nervous system (ie, tumor, inflammation, convulsive seizure, vascular disorders, Parkinson's disease, Alzheimer's disease or other type of dementia, myasthenia gravis, or other degenerative diseases).
- 21) Patients with any mental retardation or persistent neurological findings due to serious head injury.
- 22) Patients with a BMI of $\leq 18 \text{ kg/m}^2$ or $\geq 40 \text{ kg/m}^2$ at screening.
- 23) Patients with previous or existing macular or retinal pigment changes.

- 24) Patients with a previous (within 5 years prior to screening) or existing malignant tumor (excluding appropriately treated basal cell carcinoma of the skin, squamous cell carcinoma, and uterine cervix cancer).
- 25) Patients with a history of neuroleptic malignant syndrome.
- 26) Patients with severe tardive dyskinesia, severe dystonia, or other severe motor dysfunction.
- 27) Patients with an HbA1c (NGSP) value of 8.4% or higher at screening.
- 28) Patients with a history or presence of clinically significant ECG abnormality.
- 29) Patients who have received the study medication (including placebo) in a previous clinical study of SM-13496.
- 30) Patients who are breastfeeding.
- 31) Patients who are currently participating or participated in a clinical study with an investigational or marketed compound or device within 3 months prior to screening or who participated in 3 or more clinical studies within 12 months prior to screening.
- 32) Patients who are otherwise considered ineligible for the study by the investigator.

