6.4.2 Laboratory tests

Blood and urine samples for the laboratory test will be collected at Visits 1, 2, 3, 6, 8, and at discontinuation, and will be submitted to the central laboratory for analysis. At Visit 8 or at discontinuation, the samples should be collected within 72 hours after the final administration of the study drug and before the post treatment with antipsychotics. At Visits 2 and 8 or at discontinuation, blood samples will be collected in a fasting condition. Collection and handling of blood samples will be performed in accordance with the routine procedures and the separately provided instructions.

The central laboratory will analyze the samples for the tests listed in Table 6.

Table 6 Contents of the laboratory variables

Hematology	Red blood cell count, white blood cell count, hemoglobin, hematocrit, platelet count, white blood cell classification (ie, neutrophils, eosinophils, basophils, monocytes, and lymphocytes)
Blood chemistry test	AST, ALT, ALP, γ -GTP, total protein, total bilirubin, BUN, creatinine, total cholesterol, LDL cholesterol, HDL cholesterol, triglycerides, LDH, CK, blood glucose, uric acid, HbA1c, glycoalbumin, prolactin, albumin, insulin, electrolytes (Na, K, Cl),
Endocrine	Thyroid stimulating hormone (TSH), free thyroxine (FT4), total and free testosterone
Hepatitis	HBs antigen, HCV antibody (Low positive HCV antibody will be confirmed by INNO-LIA method.)
Urinalysis (qualitative tests)	Protein, glucose, urobilinogen, occult blood

Prolactin, HbA1c (NGSP), glycoalbumin, blood glucose, total cholesterol, LDL cholesterol, HDL cholesterol, and triglycerides will be measured only at Visits 1, 2 and 8 and at discontinuation. Blood glucose will be measured in fasting condition at Visits 2 and 8 and at discontinuation. TSH, FT4, and total and free testosterone will be measured only at Visits 1 and 8 and at discontinuation. Hepatitis tests will be performed only at screening.

The prolactin concentration data will not be disclosed until all the other data is locked to ensure the study blindness, as antipsychotics often increase prolactin concentrations, and will be reported to the investigators and the sponsor.

Pregnancy test (urine chorionic gonadotropin) will be performed in female patients of childbearing potential before menopause at the study site at Visits 1 and 8 and at discontinuation. If urine pregnancy test is positive, serum pregnancy test will be performed.

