9.7.6 Laboratory tests, vital signs, body weight, and 12-lead ECG

Summary statistics for laboratory tests, vital signs, body weights, and 12-lead ECG parameters will be provided by treatment group. Continuous variables will be summarized using descriptive statistics of number of patients, mean, median, standard deviation, minimum, and maximum values. Categorical variables will be reported as frequencies and percentages. Laboratory tests as a categorical variable will be reported for shift tables. A rank ANCOVA method with adjustments for baseline value will be applied to change from baseline to Week 6 (LOCF) in serum prolactin, fasting blood glucose, HbA1c (NGSP), glycoalbumin, total cholesterol, LDL cholesterol, HDL cholesterol, triglycerides, and body weight for comparison between each SM-13496 (20-60 and 80-120 mg/day) group and the placebo group.

Laboratory data will be summarized by the flagging of abnormal values in data listings. The incidence of markedly abnormal post-baseline laboratory values (MAPLV), markedly abnormal post-baseline vital signs (MAPVS), and prolonged QTc will be summarized by treatment group. In these analyses, post-baseline laboratory test values obtained at unscheduled visits will be taken into consideration.

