16.3.2. LABORATORY REFERENCE RANGES AND MARKEDLY ABNORMAL CRITERIA

Quantitative laboratory measurements will be compared with the relevant laboratory reference ranges and categorized as:

- Low: Below the lower limit of the laboratory reference range.
- Normal: Within the laboratory reference range (upper and lower limit included).
- High: Above the upper limit of the laboratory reference range.

In addition to the high and low quantitative laboratory assignments (as identified by means of the laboratory reference ranges), markedly abnormal quantitative safety (and other) laboratory assessments will also be identified. Markedly Abnormal Post-baseline Laboratory Values (MAPLV) for selected laboratory parameters can be found in Table C. The criterion of MAPLV is satisfied if a value falls into the markedly abnormal range. Patients will be represented in the count of a particular MAPLV if they have experienced that MAPLV at least once during the post-baseline double-blind phase, regardless of baseline value, up to and including LOCF endpoint. The number and percentage of patients with MAPLV will be presented by treatment group and for the combined SM-13496 group.

Table C: Criteria for Markedly Abnormal Post-Baseline Laboratory Values

Hematology Parameter	Markedly/Abnormal Range
Hemoglobin	Male: ≤ 11.5 g/dL Female: ≤ 9.5 g/dL
Hematocrit	Male: ≤ 37% Female: ≤ 32%
WBC	≤ 2.8 x 10 ⁹ /L ≥ 16 x 10 ⁹ /L
Neutrophils (percent)	≤ 15%
Eosinophils (percent)	≥ 10%
Platelet Count	≤ 75 x 10 ⁹ /L ≥ 700 x 10 ⁹ /L
Clinical Chemistry Parameter	Markedly/Abnormal Range
Alkaline Phosphatase	≥ 3 x ULN

Document: K:\DSP\SM-13496\KVA95374\Biostatistics\Documentation\SAP
 Author: [REDACTED] Version Number: 1.0
 Version Date: 30MAR2017

Template No: CS_TP_BS016 – Revision 3 Reference: CS_WI_BS005
 Effective Date: 01May2012

Copyright © 2012 [REDACTED] All rights reserved.
 The contents of this document are confidential and proprietary to [REDACTED] Unauthorized use, disclosure or reproduction is strictly prohibited.

ALT	≥ 3 x ULN
AST	≥ 3 x ULN
Total Bilirubin	≥ 2.0 mg/dL
Albumin	< 50% LLN
Glucose (fasting)	< 45 mg/dL >160 mg/dL
Sodium	< 130 mmol/L > 150 mmol/L
Potassium	< 3 mmol/L > 5.5 mmol/L
Chloride	< 90 mmol/L > 115 mmol/L
Calcium	< 8.4 mg/dL > 11.5 mg/dL
Blood Urea Nitrogen	≥ 30 mg/dL
Creatinine	≥ 2.0 mg/dL
Creatine Phosphokinase	≥ 3 x ULN
LDH	≥ 3 x ULN
HbA1c	≥ 7.5%
Prolactin	≥ 5 x ULN
Total Cholesterol (fasting)	≥ 300 mg/dL
LDL Cholesterol (fasting)	≥ 200 mg/dL

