16.5.2. VITAL SIGNS MARKEDLY ABNORMAL CRITERIA

Markedly abnormal quantitative Vital Signs measurements will be identified in accordance with the following predefined markedly abnormal criteria.

Variable	Unit	Low	High
SBP	mmHg	≤ 90 mmHg AND change from baseline ≤ -20 mmHg	≥ 180 mmHg AND change from baseline ≥ 20 mmHg
DBP	mmHg	≤ 50 mmHg AND change from ≤ -15 mmHg	≥ 105 mmHg AND change from baseline ≥ 15 mmHg
Pulse rate	Bpm	≤ 50 bpm AND change from baseline ≤ -15 bpm	≥ 120 bpm AND change from baseline ≥ 15 bpm
Body temperature	°C	NA	≥ 38.3 °C AND change from baseline ≥ 0.8 °C
Weight	Kg	percentage change from baseline ≤ -7.0 %	percentage change from baseline ≥ 7.0 %

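### The count of markedly abnormal laboratory values ignores baseline, and the HbA1c cut-off lies inside the range allowed at entry, so the table cannot separate new from pre-existing abnormality

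*SAP*

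**What the plan says.** **The counting rule.** SAP 16.3.2 applies an absolute threshold: "The criterion of MAPLV is satisfied if a value falls into the markedly abnormal range". A patient is counted "if they have experienced that MAPLV at least once during the post-baseline double-blind phase, regardless of baseline value". The output is a number and percentage by treatment group and for the combined SM-13496 group.

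**The HbA1c cut-off and entry limit.** Table C flags HbA1c at 7.5% or higher. Exclusion criterion 27 in Protocol 4.1.2 removes "Patients with an HbA1c (NGSP) value of 8.4% or higher at screening". Inclusion criterion 10 in Protocol 4.1.1 admits treated diabetes on a stable regimen: "The dose of oral hypoglycemic drugs or antihypertensive drugs remained unchanged for at least 30 days prior to screening". The entry criteria set no numeric limit for triglycerides, cholesterol or prolactin, which Table C also flags.

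**Timing.** Protocol 6.4.2 gives a short schedule for a group of tests that includes HbA1c, glucose, lipids and prolactin: "triglycerides will be measured only at Visits 1, 2 and 8 and at discontinuation". A completer thus has one scheduled post-baseline value for these tests. Protocol 9.7.6 adds unscheduled values.

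**How the summary is described.** Protocol 9.7.6: "The incidence of markedly abnormal post-baseline laboratory values (MAPLV), markedly abnormal post-baseline vital signs (MAPVS), and prolonged QTc will be summarized by treatment group".

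**Where baseline is used.** The vital-sign criteria in SAP 16.5.2 include a change from baseline, for example systolic pressure "≥ 180 mmHg AND change from baseline ≥ 20 mmHg". SAP 16.7.4 defines emergence of suicidal ideation as absent at baseline and present afterwards. For laboratory data, SAP 16.3 plans change from baseline by visit, shift tables on the normal range, a rank ANCOVA on change for selected tests, and a listing of patients who meet the markedly abnormal criteria.

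**The concern.** A reader of a table of markedly abnormal post-baseline values wants to know how many patients became markedly abnormal on treatment. This table mixes those patients with others who arrived in that state and did not change. HbA1c shows the problem most clearly, because the entry limit itself admits patients above the cut-off.

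Glucose metabolism, lipid metabolism and prolactin are named secondary safety objectives. If several counted patients were already abnormal at entry, the percentages overstate new abnormality in every arm and any ratio between arms moves towards 1. When counts are small, a chance imbalance in carried-in patients could look like a drug signal or mask one. The summary tables give no means of telling which has happened.

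**Working it through.** The plan states no figure for this point, so there is none to reproduce. The check has four steps.

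**1. The overlap.** The Table C cut-off is 7.5% or above, and entry is allowed below 8.4% at screening. The overlap is 8.4 − 7.5 = 0.9 percentage points (7.5 to 8.3 at one decimal). An unchanged patient in this window meets the criterion. Because the limit applies at screening while baseline is the last value on or before Day 1 (SAP 6.2), baseline is not strictly capped at 8.4%.

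**2. Whether another planned table separates the cases.** Take one patient who goes from 7.0% to 7.6% and another who stays at 7.9%. If all these values exceed the laboratory's upper reference limit, both appear as high-to-high in the shift table, and both count once as an HbA1c MAPLV. The rank ANCOVA compares ranked change and counts nobody crossing a threshold. Only the patient listings tell the two apart.

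**3. Effect on the reported percentages.** Let b be the share already at or above the cut-off at baseline who stay there, and r the new-onset rate in the rest. Reported percentage = b + (1 − b) × r. A count restricted to patients below the cut-off at baseline would report r. The documents give neither b nor r. Assume r = 1% on placebo and 3% on active, with the planned 167 per arm (Protocol 3.5):

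| b (assumed) | Carried in, per arm | Placebo | Active | Ratio | Difference |
|---|---|---|---|---|---|
| 0% | 0 | 1.00% | 3.00% | 3.0 | 2.00 points |
| 1% | 1.7 | 1.99% | 3.97% | 2.0 | 1.98 points |
| 2% | 3.3 | 2.98% | 4.94% | 1.7 | 1.96 points |
| 5% | 8.4 | 5.95% | 7.85% | 1.3 | 1.90 points |

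For b = 2%, placebo is 0.02 + 0.98 × 0.01 = 0.0298 and active is 0.02 + 0.98 × 0.03 = 0.0494. The ratio shrinks markedly; the difference hardly moves.

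For chance imbalance, treat the carried-in counts in two arms as independent binomials (167, b). The probability that they differ by 3 or more is 16% at b = 1% and 32% at b = 2%. The assumed true excess is 0.02 × 167 = 3.3 patients.

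**4. How often unchanged patients are flagged.** All inputs here are assumptions, with no drug effect.

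- *HbA1c*: within-patient SD (w) 0.15 to 0.25 points; post-baseline value = baseline + N(0, 2w²). With baseline uniform over 7.5 to 8.4, the flagging probability is 0.91 (w = 0.15) or 0.84 (w = 0.25). If baseline density instead falls away from 7.5 (exponential, mean 0.2 to 0.45 points), it is 68–83%. If true values fall exponentially and both visits carry error, it is 37–78%. Each figure is conditional on entering in the window.
- *Fasting triglycerides* (cut-off 300 mg/dL): median 110 to 120 mg/dL, between-patient log SD 0.50 to 0.55, within-patient log SD 0.20. The share flagged is 3.1–5.9%, and 54–62% of those flagged were already at or above 300 at baseline (0.017/0.031 and 0.036/0.059, before rounding).

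**The case against.** **The rule is disclosed.** The SAP calls these values post-baseline, never treatment-emergent, and says outright that baseline is ignored. A reader might infer that the SAP contradicts the protocol by delivering prevalence where incidence was promised. The documents do not support that: Protocol 9.7.6 uses the same post-baseline label, and SAP 16.3 also uses incidence loosely, for urinalysis values outside the normal range. This objection stands; it is an analysis choice, not an inconsistency.

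**The objectives do not rest on this table.** The glucose, lipid and prolactin objectives concern change from baseline at the final assessment, analysed by rank ANCOVA with baseline adjustment. That stands.

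**No ratio is planned.** SAP 16 plans no between-group comparison of safety data unless specified, and none is specified for MAPLV. The ratios in the working describe what a reader may compute, and the difference is nearly unaffected. That stands.

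**Other safeguards exist.** Patients meeting the criteria are listed. Clinically significant laboratory abnormalities are recorded as adverse events, and metabolic treatment-emergent events are summarised. These help, but listings need patient-by-patient reading and adverse-event reporting depends on the investigator's judgement. Neither gives a count of new crossings at the Table C cut-offs.

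**Other criteria ignore baseline too.** The ECG limits and the absolute QTc categories carry no baseline condition. True, although QTc also has separate change-from-baseline categories; the laboratory criteria have no such companion.

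**A baseline condition does not remove noise.** In the triglyceride model, 38–46% of flagged patients were below 300 at baseline, so about 1.5–2.4% of patients below the cut-off at baseline would appear as new with no drug effect. That stands as a limit of the fix.

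**Conclusion.** The concern holds as a limited one. The laboratory MAPLV count ignores baseline, the HbA1c cut-off falls inside the entry range, and no planned summary table separates new from pre-existing values at these cut-offs.

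The consequence is for the interpretation of a descriptive table. A reader might infer that the metabolic safety conclusions are biased, or that the arm comparison is distorted. The documents do not support that: carried-in cases are balanced in expectation by 1:1:1 randomisation, the difference moves only from 2.0 to 1.9 points even at an assumed 5% carried-in share, and the rank ANCOVA is unaffected. What remains is inflated percentages in all arms, ratios drawn towards 1, and some exposure to chance imbalance when counts are small.

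The size in this trial is unknown. The documents give no baseline distribution, and few patients may fall in the window. The table in step 3 rests on assumed carried-in shares and new-onset rates, with every carried-in patient staying above the cut-off. The HbA1c flagging probabilities depend heavily on the assumed baseline shape.

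**What to change.** In SAP 16.3.2, keep the existing count and add a treatment-emergent count for each Table C parameter: patients who meet the criterion post-baseline and do not meet it at baseline. The denominator is patients who do not meet it at baseline and have a post-baseline value. Keeping the existing count beside it retains worsening from an already abnormal baseline; there is no need to demote that count.

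The cost is SAP wording and one more row per parameter, using data already collected. No protocol change, extra sampling or alpha is involved. The drawbacks are a longer table, a separate denominator for each parameter, and some crossings counted as new that reflect only within-patient variation. For the tests with a single scheduled post-baseline draw, the schedule offers no confirmatory value to reduce that.

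### SAP Table C screens neutrophils by percentage only, so an absolute count just above 0.42 x 10^9/L can go unflagged while a count of 1.8 x 10^9/L at WBC 12 is flagged

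*SAP*

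**What the plan says.** SAP 16.3.2 sorts each quantitative laboratory result against the laboratory's reference range; the lowest category is "Low: Below the lower limit of the laboratory reference range". It then applies the fixed limits of Table C. For neutrophils there is one row, "Neutrophils (percent", with a limit of 15% or less. The only other row that could pick up a low neutrophil count is WBC, flagged at 2.8 x 10^9/L or below (and, on the high side, at 16 or above).

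Rows are applied one at a time: "The criterion of MAPLV is satisfied if a value falls into the markedly abnormal range". A patient is counted if this happens at least once after baseline, "regardless of baseline value, up to and including LOCF endpoint". SAP 16.3 uses these flags for a summary of patients meeting the criteria and for a listing.

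Neither document gives an absolute neutrophil criterion or a rule joining WBC to the percentage. Both ingredients are collected: the hematology line of Protocol 6.4.2, Table 6, includes the white cell count and the "white blood cell classification (ie, neutrophils, eosinophils, basophils, monocytes, and lymphocytes" breakdown.

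**The concern.** A neutrophil percentage depends on the other white cells as well as on the neutrophils. Fixing the limit at 15% is the same as using a count limit that slides with WBC: low where WBC is low, high where WBC is high. The WBC row closes the gap only at 2.8 and below. Just above that value, a patient can have a very small neutrophil count and meet neither criterion.

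At stake is one line of the safety tables. A reader who takes the neutrophil row as the trial's account of marked falls in neutrophils could see no cases, or see cases ranked in the wrong order, although the data needed to show otherwise were collected.

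**Working it through.** The documents state no neutrophil count, so there is no plan figure to reproduce. The check applies Table C as written.

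**Inputs (SAP 16.3.2, Table C).** Neutrophils flagged at <= 15%; WBC flagged at <= 2.8 or >= 16 x 10^9/L. All limits are inclusive.

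**Formula.** Absolute neutrophil count (ANC) = WBC x neutrophil % / 100, in 10^9/L.

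**Step 1: the lower limit of what can be missed.** To escape both rows a patient needs WBC above 2.8 and neutrophils above 15%. The bound is 2.8 x 15 / 100 = 0.42. Because both limits are inclusive, WBC 2.8 with 15% (exactly 0.42) is flagged by both rows; only counts above 0.42 can escape.

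How close to 0.42 depends on reporting precision, which the documents do not give. The range over plausible assumptions is:

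| WBC reported to | Neutrophil % reported to | Lowest unflagged pair | ANC |
|---|---|---|---|
| 0.1 | 1 | 2.9 with 16% | 0.464 |
| 0.1 | 0.1 | 2.9 with 15.1% | 0.438 |
| 0.01 | 0.1 | 2.81 with 15.1% | 0.424 |

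**Step 2: the gap is not confined to the edge.** WBC 3.0 with 16% gives 0.48, and WBC 6.0 with 16% gives 0.96. Neither is flagged.

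**Step 3: the other end.** WBC 12 with 15% gives 12 x 15 / 100 = 1.80, which the neutrophil row flags. A count of 1.80 meets that row only when WBC is at least 1.80 / 0.15 = 12.0; the same count at WBC 4.0 (45%) is not flagged. At WBC 15.9 with 15% the flagged count is 2.385, and the WBC row is still silent.

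**Step 4: compare.** The flagged patient at 1.80 has 1.80 / 0.464 = 3.9 times the neutrophils of the unflagged patient at 0.464. Between WBC 2.8 and 16, the count at which the 15% row takes effect moves from 0.42 to 16 x 0.15 = 2.40, a factor of 2.40 / 0.42 = 5.7.

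**The case against.** The strongest reply is that nothing here contradicts the protocol. Protocol 9.7.6 calls for the incidence of MAPLV without defining the limits, so the SAP was free to choose a percentage. The row is labelled as a percentage, and 15% at WBC 12 is an abnormal differential by that label. This stands: the second example is a false positive only if the row is read as a screen for low neutrophil counts. It shows that the row does not order patients by count; it does not show that the row fails on its own terms.

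A reader might infer that marked falls would go unseen altogether. The documents do not support that:

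- The investigator must judge every out-of-range laboratory value and record clinically significant ones as adverse events (Protocol 6.4.1.2). Events are graded for severity (Protocol 6.4.1.3) and tabulated by maximum severity (SAP 16.1.1).
- Abnormal values are flagged in the listings (Protocol 9.7.6).
- By-visit summaries carry a minimum and maximum (SAP 8 and 16.3).
- Shift tables show movement to Low (SAP 16.3).

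Each covers the gap only in part. Grading by investigators is judgement at each site, not a uniform limit. The shift table has no grades within Low. The minimum percentage and the minimum WBC may come from different patients, so together they do not reveal the lowest count. If the central laboratory also reports absolute neutrophils, the by-visit minimum would show that count directly; the documents do not say whether it does.

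A reader might also want a miss rate, such as the share of low percentages that escapes both rows. That needs a severity band and a distribution of neutrophil percentages, and the documents give neither. A share of the percentage scale is not a share of patients.

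**Conclusion.** The point holds as a limited one. Followed exactly, Table C can leave a neutrophil count just above 0.42 x 10^9/L unflagged (0.464 at ordinary reporting precision, which is an assumption) while counting 1.80 at WBC 12 as markedly abnormal. MAPLV is the SAP's only pre-specified numeric severity screen for low neutrophils. It is not the only route by which a severe fall could come to light.

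The practical size is small. Few patients are likely to fall in the gap in a trial planned for 501. Neither document describes a hematological signal, and Protocol 1 reports no notable safety issues from the two earlier bipolar studies. No efficacy result is affected. The arithmetic rests only on Table C. The one judgement from outside the documents is that the absolute count is what a reader of a neutrophil safety row wants to know. This is a worthwhile, optional improvement to safety reporting, not an inconsistency in the plan.

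**What to change.** Add to SAP Table C a derived row for absolute neutrophil count = WBC x neutrophil % / 100, taking both results from the same sample, and use it in the MAPLV count and listing. The sponsor's medical reviewer should fix its low cut-off before unblinding; no value is proposed here. Keep the percentage row so that results remain comparable with outputs that use the current criteria.

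The cost is one derived variable and one table row. No new sampling is needed: WBC and the differential belong to the same hematology panel, for which five samples per patient are planned (Protocol 6.4.7, Table 7). The SAP already derives a laboratory variable from the product of two results, HOMA-IR in 16.3.1. The downside is one criterion that is not in the current Table C set.
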